9.5 Dose Modifications

Neutropenia was the most frequently reported adverse reaction in palbociclib clinical trials, with an incidence of 80% to 83%. A Grade \geq 3 decrease in neutrophil counts was reported in 66% of patients receiving palbociclib plus letrozole or fulvestrant. The median time to first episode of any grade neutropenia was 15 days and the median duration of Grade \geq 3 neutropenia was 7 days.

Febrile neutropenia has been reported in 1.8% of patients exposed to palbociclib across studies. Physicians should inform patients to promptly report any episodes of fever.

Management of severe or intolerable adverse reactions may require temporary dose reduction and/or interruption of palbociclib and/or H3B-6545.

Recommendations for dose reduction, interruption or discontinuation of either drug in the management of adverse reactions are summarized in Table 5 (hematologic toxicities) and

 Table 6 (non-hematologic toxicities).
 Clinical judgment of the treating physician should guide the management plan of each patient based on individual benefit/risk assessment.

Two dose reductions of H3B-6545 (450 mg to 300 mg, and then to 150 mg QD) for toxicity will be allowed as per the guidance summarized in Table 5 and Table 6. If persistent toxicity occurs despite 2 dose reductions, the subject will discontinue study treatment.

Two dose reductions for palbociclib (125 mg to 100 mg, and then to 75 mg QD) for toxicity will be allowed (Table 5 and Table 6). If persistent toxicity occurs despite 2 dose reductions, the subject will discontinue study treatment.

Hematologic toxicities

Monitor complete blood cell (CBC) counts prior to the start of palbociclib therapy and at the beginning of each cycle, as well as on Day 15 of the first 2 cycles, and as clinically indicated. For patients who experience a maximum of Grade 1 or 2 neutropenia in the first 6 cycles, monitor CBC counts for subsequent cycles every 3 months, prior to the beginning of a cycle and as clinically indicated.

CTCAE Grade	Palbociclib	H3B-6545
Anemia		
Grade 4	Withhold dose until recovery to Grade ≤2; resume drug at next lower dose	Withhold dose until recovery to Grade ≤2; resume drug at next lower dose

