Grade 3	 Day 1 of cycle: Withhold drug, repeat complete blood cell count monitoring within 1 week. When recovered to Grade ≤2, start the next cycle at the same dose. Day 15 of first 2 cycles: Continue palbociclib at current dose to complete cycle and repeat complete blood cell count on Day 22. 	Withhold dose until recovery to Grade ≤2; resume drug at next lower dose
Grade 1 or 2	No dose adjustment is required	No dose adjustment is required
All other hematological toxicity		
Grade 4	Withhold dose until recovery to Grade ≤2; resume drug at next lower dose	No dose adjustment is required.
Grade 3	• Day 1 of cycle: Withhold drug, repeat complete blood cell count monitoring within 1 week. When recovered to Grade ≤2, start the next cycle at the same dose.	No dose adjustment is required.

Table 5Dose Modifications and Management Recommendation –Hematologic Toxicities
	• Day 15 of first 2 cycles: Continue palbociclib at current dose to complete cycle and repeat complete blood cell count on Day 22.	
Grade 1 or 2	No dose adjustment is required	No dose adjustment is required
Grade 3 neutropenia with fever ≥38.5 °C and/or infection	Withhold palbociclib until recovery to Grade ≤ 2 ; resume at the next lower dose	Withhold dose until fever subsides; resume at the same dose

CTCAE = Common Terminology Criteria for Adverse Events.

a. Laboratory values that meet criteria listed in this table should be repeated and confirmed within 24 hours of the initial results being reported.

b. Subjects who do not receive at least 75% of the dose for reasons other than toxicity (eg, withdrawal of consent, physician decision, lost to follow-up, etc.) will not be considered evaluable for DLT

Nonhematologic Toxicities

Table 6Dose Modifications and Management Recommendation –Nonhematologic Toxicities

CTCAE Grade	Palbociclib	H3B-6545
Sinus bradycardia		
Grade 1 (asymptomatic) Heart rate ≥40 bpm	No dose adjustment is required	No dose adjustment is required
Grade 1 (asymptomatic) Heart rate <40 bpm	No dose adjustment is required	First occurrence: Withhold drug until heart rate is ≥50 bpm; resume drug at the same dose level
		Second occurrence: Withhold drug until heart rate is ≥50 bpm; resume drug at the next lower dose
Grade 2 (symptomatic, intervention not indicated; change in medication initiated)	No dose adjustment is required	Withhold drug until (a) symptoms resolve and (b) heart rate is \geq 50 bpm; resume drug at the next lower dose

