Grade 3 (symptomatic, intervention indicated)	Withhold palbociclib until (a) symptoms resolve and (b) heart rate is \geq 50 bpm; resume drug at the next lower dose	Withhold drug until (a) symptoms resolve and (b) heart rate is \geq 50 bpm; resume drug at the next lower dose
Grade 4 (Life-threatening consequences; urgent intervention indicated)	Withhold palbociclib until (a) symptoms resolve and (b) heart rate is \geq 50 bpm; resume drug at the next lower dose	Discontinue drug
QTcF prolongation		-
Grade 1 (average: 450 – 480 ms)	No dose adjustment is required	No dose adjustment is required

Grade 2	No dose adjustment is required	No dose adjustment is required
(average: 481 – 500 ms)		Repeat assessment after 1 week; if the average is still between 481 and 500 mg, decrease to the next lower dose
Grade 3 (average: ≥501 ms; >60 ms change from baseline)	Withhold drug until average is <480 ms and <60 ms change from baseline; resume at the next lower dose	Withhold drug until average is <480 ms and <60 ms change from baseline; resume at the next lower dose
Grade 4 (Torsade de pointes; polymorphic ventricular tachycardia; signs/symptoms of serious arrhythmia)	Discontinue drug	Discontinue drug
Other		
Grade 1 or 2	No dose adjustment is required	No dose adjustment is required
Grade 3 or 4 (if persisting despite optimal medical care)	Withhold palbociclib until symptoms resolve to Grade ≤2; resume drug at the next lower dose	Withhold drug until symptoms resolve to Grade ≤ 2 ; resume drug at the next lower dose

CTCAE = Common Terminology Criteria for Adverse Events; QTcF = QT interval corrected for heart rate using Fridericia's formula.

Monitor subjects for pulmonary symptoms indicative of ILD/pneumonitis (eg, hypoxia, cough, dyspnea). In patients who have new or worsening respiratory symptoms and are suspected to have developed ILD/pneumonitis, interrupt palbociclib immediately and evaluate the subject. Permanently discontinue palbociclib in subjects with severe ILD or pneumonitis.

Dose modifications for use with strong CYP3A inhibitors

Avoid concomitant use of strong CYP3A inhibitors and consider an alternative concomitant medication with no or minimal CYP3A inhibition. If patients must be co-administered a strong CYP3A inhibitor:

- Reduce the palbociclib dose to 75 mg QD
- Reduce the H3B-6545 dose to 150 mg QD

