5.6.1 Extent of Exposure

Exposure will be summarized descriptively by drugs for the Safety Analysis Set, including the following parameters defined per subject:

• Duration of treatment (in months), defined as (date of last dose – date of first dose +1)/30.4375, regardless of drug interruptions.

Eisai Confidential Page 16 of 30

- Total dose received (mg) by drug (H3B-6545, or palbociclib)
- Actual Dose Intensity (ADI, mg/day) by drug (H3B-6545, or palbociclib): total dose received (mg)/duration of treatment (days).

In addition, number of patients with dose reduction and dose interruption will be summarized.

A dose reduction of H3B-6545 or palbociclib (respectively) refers to the situation when the administration of H3B-6545 or palbociclib (respectively) was reduced 1 level lower. For H3B-6545, dose interruptions are identified by 0 doses, which are preceded and followed by the same dose level. If the dose after the 0 dose is lower than that before the 0 dose, this dose change will be counted as a dose reduction.

A by-patient listing of the date of study drug administration and the dose administered will be presented. Patients experiencing any dose modification (eg, increase, reduction, or interruption), together with the reasons for dose modification, will also be provided in a separate listing.

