5.6.6 Electrocardiograms

Central triplicate 12-lead ECG are collected at Screening, and on Day 1, Day 8, Day 15, Day 21 and Day 28 of Cycle 1, Day 1 of Cycle 2 or above, at the End of Treatment visit, or at the safety follow up visit. Local ECG may also be performed.

For each ECG parameter (QTcF, PR interval, etc), the average of triplicate at each timepoint (screening, predose and postdose at scheduled visits, end of treatment [EOT], unscheduled visits, etc) will be used in ECG analysis below:

• By-timepoint analysis: ECG parameters numerical results and changes from baseline at each scheduled timepoints (including EOT and safety follow up visit) during the treatment period will be summarized by treatment groups.

Eisai Confidential Page 20 of 30

• Categorical analysis: the number (percentage) of subjects who meet the following criterion with at least 1 post-baseline ECG result during the treatment period will be summarized (based on worst post-baseline results) and presented by treatment groups (Table 4):

Table 4 Criteria for Categorical Analysis of ECG Parameters

ECG parameter	Criteria		
QTcF	>450 and ≤480 msec		
	>480 and ≤500 msec		
	>500 msec		
	Change from baseline >30 and ≤60 msec		
	Change from baseline >60 msec		
	>500 msec or change from baseline >60 msec		
PR interval	Change-from-baseline >25% resulting in PR >200 msec		
QRS Change-from-baseline >25% resulting in QRS >120 msec			
HR	Changes reflecting a more than 25% decrease from baseline to a HR <50 bpm		
	Changes reflecting a more than 25% decrease from baseline to a HR <40 bpm		
	Changes reflecting a more than 25% increase from baseline to a HR >100 bpm		

ECG = electrocardiogram, HR = heart rate, QTcF = QT interval corrected for heart rate using Fridericia's formula.

Shift tables will present changes in ECG interpretation (categorized as normal; abnormal, not clinically significant; and abnormal, clinically significant) from baseline to worst post-baseline reading; if multiple interpretation records are collected in triplicate on Day 1 predose, the worst interpretation (eg, abnormal is worse than normal) prior to the first dose will be used as baseline interpretation.

All ECG data, including central and local 12-lead ECG data, will be listed. All ECG abnormalities based on central/local 12-lead ECG will also be listed.

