Pharmacokinetic assessments: The lower limit of quantification (LLOQ) in plasma is 1.00 ng/mL for palbociclib and 1.00 ng/mL for H3B-6545, respectively. While calculating PK parameters, below lower quantification (BLQ) values will be handled according to 302-104.01-MNL. When developing individual concentration-time profiles, BLQ values will be handled according to 302-104.01-MNL. The handling of anomalous concentration values will follow 302-104.01-MNL. When presenting individual/raw (raw, hereafter) values and summary statistics, the following rule will be applied for drug concentrations and PK parameters.

Typical variable	Unit	N	Digit rule	Raw Minimum Maximum	Mean Median	Standard deviation	Geometric Mean	CV (%)
Plasma concentration	ng/mL	X	Significant digits	3	3	3	_	ı
C _{max}	ng/mL	X	Significant digits	3	3	3	3	3
t _{max}	h	X	Fixed decimal places	2	2	ı	_	ı
AUC	ng•h/mL	X	Significant digits	3	3	3	3	3
CL/F	L/h	X	Significant digits	3	3	3	3	3
Ratio of exposure index	No units	X	Significant digits	3	3	3	3	3

Eisai Confidential Page 23 of 30

Individual pharmacokinetic data: The following data will not be included in the calculation of summary statistics.

- Plasma concentration data at predose if the blood samples are collected after administration
- PK data (plasma concentrations and PK parameters) in a patient with any dose modification (increase, reduction, or interruption) within 3 days prior to the blood sampling.
 - ie, The following PK data will not be included in the calculation of summary statistics;
 - PK data of palbociclib from a patient with dose modification in palbociclib from C1D5 to C1D8
 - PK data of palbociclib and H3B-6545 from a patient with dose modification in palbociclib or H3B-6545 from C1D18 to C1D21
 - PK data of H3B-6545 from a patient with dose modification in H3B-6545 from C1D25 to C1D28
- Dosing and sampling date/time are missing

The following case will be determined individually:

• Significant deviation from the allowance of PK blood sampling schedule

Further definitions and conventions for data handling will be presented in "Programming Specifications".

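### The SAP's 3-day PK exclusion windows can let a DDI ratio compare two days at different doses of the measured drug, and no same-dose or normalisation rule is stated (low priority)

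*SAP*

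**What the plan says.** Protocol 9.8.1.7.1 and SAP 5.5.1 define the DDI effect as a within-subject ratio of Cmax, AUC(0-24h) and C24 in the escalation cohorts. For palbociclib it is Cycle 1 Day 21 over Day 8; for H3B-6545 it is Day 21 over Day 28. The ratios are summarised by cohort, and each cohort has 6 DLT-evaluable subjects.

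SAP Section 8 lists the PK data to be left out of summary statistics. For dose changes, the rule covers data "in a patient with any dose modification (increase, reduction, or interruption) within 3 days prior to the blood sampling". It then gives the windows: palbociclib D5-D8 for the Day 8 data, either drug D18-D21 for the Day 21 data, and H3B-6545 D25-D28 for the Day 28 data. Only significant departures from the sampling schedule are left to case-by-case decision.

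Protocol 9.5 permits reductions during Cycle 1. For H3B-6545: "Two dose reductions of H3B-6545 (450 mg to 300 mg, and then to 150 mg QD) for toxicity will be allowed". For palbociclib the steps are 125, 100 and 75 mg. For Grade 2 QTcF prolongation, the H3B-6545 instruction is: "Repeat assessment after 1 week; if the average is still between 481 and 500 mg, decrease to the next lower dose" (the text prints mg where ms must be meant).

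**The concern.** A within-subject ratio isolates the partner drug's effect only if the measured drug is given at the same dose on both days. The Section 8 windows test each sampling day on its own. A reduction that falls between the paired days, but outside both windows, passes the screen and enters the ratio as if it were an interaction.

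The direction is predictable. An H3B-6545 cut after Day 21 raises Day 21/Day 28 and looks like palbociclib increasing H3B-6545 exposure. A palbociclib cut after Day 8 lowers Day 21/Day 8 and looks like H3B-6545 reducing palbociclib exposure. The DDI ratio is a named secondary endpoint. Day 8 and Day 28 profiles are taken only in escalation, and SAP 3.2 says no expansion subjects will be enrolled, so these small cohorts are the study's only source for it.

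**Working it through.** **1. Reproduce the windows.** Sampling day minus 3 gives the first day of each: 8-3 = 5, 21-3 = 18, 28-3 = 25. These match SAP Section 8.

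**2. Find the unscreened days.** Let the new dose apply from day d onward, and read the rule as the date of change.
- Palbociclib: the Day 8 and Day 21 doses differ for d = 9 to 21 (13 days). The window D18-D21 removes four. Left: **D9-D17**, 9 of 13 days.
- H3B-6545: the Day 21 and Day 28 doses differ for d = 22 to 28 (7 days). The window D25-D28 removes four. Left: **D22-D24**, 3 of 7 days.

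The 24-hour sample must precede the next day's dose (Protocol 9.6.1.3.1), so a change on D9 or D22 leaves the Day 8 or Day 21 profile wholly at the old dose. Dose increases are not at issue, because intrasubject escalation starts only after Cycle 3.

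**3. Can the protocol lead there?**
- QTcF: H3B-6545 starts on D9. SAP 5.6.6 says "Central triplicate 12-lead ECG are collected at Screening, and on Day 1, Day 8, Day 15, Day 21 and Day 28 of Cycle 1", so D15 is the first scheduled ECG on the drug. A repeat one week later falls on 15+7 = D22, the first unscreened day, and the Grade 2 rule reduces the dose without a hold.
- Neutropenia: for Grade 4 on the D8 blood count, the palbociclib instruction is "Withhold dose until recovery to Grade ≤2; resume drug at next lower dose". With a hold from D9 and the 7-day median duration of Grade 3 or worse given in Protocol 9.5, dosing resumes at the lower level at about 9+7 = D16. This should be uncommon: "The median time to first episode of any grade neutropenia was 15 days". If it is first found on D15, then 15+7 = 22, and the hold would still be running in D18-D21, with zero doses inside the window.

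**4. Size for one subject.** Assume exposure is proportional to dose, the later day fully reflects the new dose, and the true ratio is 1.0. Then r = new/old dose for palbociclib (D21/D8) and r = old/new dose for H3B-6545 (D21/D28).

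**5. Size for a cohort.** A subject reduced for toxicity is not replaced, because the 75% rule in Protocol 9.1 applies only to reasons other than toxicity. So n = 6, with the other five at 1.0. Arithmetic mean = (5 + r)/6; geometric mean = r^(1/6).

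| Reduction (mg) | r | Arithmetic mean | Shift | Geometric mean | Shift |
|---|---|---|---|---|---|
| Palbociclib 125 to 100 | 0.80 | 5.80/6 = 0.967 | -3.3% | 0.963 | -3.7% |
| Palbociclib 100 to 75 | 0.75 | 5.75/6 = 0.958 | -4.2% | 0.953 | -4.7% |
| H3B-6545 450 to 300 | 1.5 | 6.5/6 = 1.083 | +8.3% | 1.070 | +7.0% |
| H3B-6545 300 to 150 | 2.0 | 7.0/6 = 1.167 | +16.7% | 1.122 | +12.2% |

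SAP 5.5.1 lists the arithmetic mean for the ratio; the protocol also lists the geometric mean. In this illustration the median stays at 1.0.

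**The case against.** *The rule may mean being on a modified dose during the window, not changing dose in it.* On that reading the cases above are caught. The SAP does not say which it means. The date reading is the more natural: if being on a modified dose were enough, a 3-day look-back would do little. SAP 5.6.1 also treats a reduction as an event ("this dose change will be counted as a dose reduction") and identifies H3B-6545 interruptions by zero doses. That support is modest, because 5.6.1 concerns exposure counts and not PK windows. The ambiguity stands.

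*The rule may be written elsewhere.* This also stands. SAP 5.5.1 sends PK parameter derivation to the sponsor's non-compartmental manual, SAP Sections 8 and 9 send further conventions to programming specifications, and the PK Analysis Set refers to valid concentrations without defining them. None of these documents is supplied. A reader might infer that the trial has no protection at all. The documents show only that the protocol and SAP state none.

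*The routes are narrow and the consequence small.* The D21 ECG could serve as the QTcF repeat, and a reduction recorded with that date would be screened. The documents give no frequency for either route. The ratios are descriptive, with no confidence interval or no-effect bounds, and the minimum, maximum and dose-modification listing would expose an affected subject. All of this is accepted, and it is why the priority is low.

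**Conclusion.** The point holds in a narrow form. Applied as listed, and read as the date of change, the Section 8 exclusions can leave a DDI ratio that reflects a dose cut in the cohort summary. The size is that of the table: a few percent on the mean for palbociclib and +8.3% or +16.7% for H3B-6545, for one affected subject in six. These figures are illustrations and not bounds. They rest on dose proportionality, which the documents do not establish, and on a true ratio of 1.0.

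A reader might go further and point to the protocol's provision that begins "If patients must be co-administered a strong CYP3A inhibitor", which cuts palbociclib to 75 mg and H3B-6545 to 150 mg and so implies larger shifts and a third drug in the ratio. The documents do not support a figure for that. They give no inhibitor effect, which could offset or outweigh the cut; strong inhibitors are excluded at entry and to be avoided on study. It is a separate matter from pairing two days at one dose.

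**What to change.** Add to the SAP Section 8 exclusions, for the DDI-ratio summary only: ratios where the dose of the drug being measured differed between the two paired sampling days; these are listed separately.

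This is one line and uses dosing records already collected. The cost is the loss of an occasional ratio from a cohort of about 6. Dose normalisation would keep those ratios, but only by assuming dose proportionality.

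The line does not settle what the SAP means by a dose modification. For example, an H3B-6545 reduction on D10-D17 puts Day 21 and Day 28 at the same lower dose. The new line keeps that ratio, while the existing rule keeps or drops it depending on the reading. That comparison is like for like in dose, so it lies outside this point.

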9 PROGRAMMING SPECIFICATIONS

The rules for programming derivations and dataset specifications are provided in separate documents.

10 STATISTICAL SOFTWARE

All statistical analyses will be performed using Statistical Analysis System (SAS) version 9.4 or later (SAS Insitute, 2002), and Phoenix WinNonlin version 7.0 or later.

11 MOCK TABLES, LISTINGS, AND GRAPHS

The study tables, listings and graphs (TLGs) shells will be provided in a separate document, which will show the content and format of all tables, listings, and graphs in detail.

13 APPENDICES

13.1 General rules deriving best overall response (BOR)

The best overall response (BOR) is determined once all the data for the subject is known. For this study, a confirmation of complete responses or partial responses is required ≥4 weeks after the initial assessment of response. In order for SD to be considered the best overall response, it must occur ≥7 weeks following the first dose of study drug. For subjects who does not have target lesion at baseline, a timepoint response of Non-CR/Non-PD will be treated as SD in BOR derivation, and will be included in DCR and CBR calculation

To program the BOR per RECIST, the rules below will be followed:

- 1. The tumor response data collected via the CRFs will be used; and
- 2. Any further response assessments after the first PD identified will not be considered for the BOR determination, however they will be presented in the data listings; and
- 3. Any tumor assessments after the subject starts a new anti-cancer therapy will not be considered; and
- 4. If there are 2 or more consecutive missing adequate tumor assessments, all subsequent assessments will not be considered for the determination of BOR.

Note that the duration between 2 adequate tumor assessments, as well as the duration between the last adequate tumor assessment and death or PD, will be used to identify the cases where 2 or more consecutive tumor assessments are missing. Using the start day and the end day to denote the study days of the 2 endpoints of the duration, duration = end day – start day. If the duration is longer than 16 weeks +2x7 days (tumor assessment window) – 1 day (ie, 125 days), then it is considered that 2 or more consecutive adequate tumor assessments are missing.

Table 5 General Rules Deriving BOR per RECIST 1.1

Timepoint 1 Overall Response	Timepoint 2 (≥4 weeks since Timepoint 1) Overall Response	BOR ^b
CR	CR	CR
CR	PR	SD, PD or PR If a CR is truly met at first time point, then any disease seen at a subsequent time point, even disease meeting PR criteria relative to baseline, makes the disease PD at that point (since disease must have reappeared after CR). Best response would depend on whether minimum duration for SD was met. However, sometimes 'CR' may be claimed when subsequent scans suggest small lesions were likely still

Eisai Confidential Page 26 of 30

		present and in fact the subject had PR, not CR at the first time point. Under these circumstances, the original CR should be changed to PR and the best response is PR.
CR	SD/PD	SD if duration of SD ≥7 weeks, otherwise PD
CR	NE	SD if duration of SD ≥7 weeks, otherwise NE. In a special case, if CR is at the next timepoint after NE, BOR will be CR.
CR ^a		SD if duration of SD ≥7 weeks, otherwise NE
PR	CR/PR	PR
PR	SD/PD	SD if duration of SD ≥7 weeks, otherwise PD
PR	NE	SD if duration of SD ≥7 weeks, otherwise NE. In a special case, if PR or CR is at the next timepoint after NE, BOR will be PR.
PR ^a		SD if duration of SD ≥7 weeks, otherwise NE
SD	Any response	SD if duration of SD ≥7 weeks, otherwise PD
PD		PD
NE		NE if the subject did not have a post-baseline tumor assessment, or if the subject only had one post-baseline tumor assessment of an early SD (duration <7 weeks) as the overall response, or post-baseline tumor assessments are not evaluable (ie, recorded as 'NE' as overall responses via the CRF)
UNK		UNK if the subject did not have a baseline tumor assessment

BOR = best overall response, CR = complete response, CRF = case report form, NE = not evaluable, PD = disease progression, PR = partial response, SD = stable disease, UNK = unknown.

13.2 **PFS Censoring rules**

For the main analysis of PFS, the censoring rules in this SAP and definition of progression date follow the principles of the FDA *Guidance for Industry: Clinical Trial Endpoints for the Approval of Cancer Drugs and Biologics* (2018). Table 6 below shows the censoring rules for the derivation of PFS.

Eisai Confidential Page 27 of 30

a: If this was the only tumor response assessment (eg, study treatment was discontinued).

b: For subjects who does not have target lesion at baseline, a timepoint response of Non-CR/Non-PD will be treated as SD in BOR derivation.

Table 6 Censoring Rules for the Derivation of PFS in Primary Analysis

No.	Situation	Date of Event (Progression/Death) or Censoring	Outcome
	No baseline or post-baseline tumor assessments	Date of first dose	Censored
2	Progression documented between scheduled visits	Date of first radiologic PD assessment	Event
3		Date of last adequate radiologic assessment prior to or on date of data cutoff	Censored
4	New anticancer treatment started	Date of last adequate radiologic assessment prior to or on date of new anticancer treatment	Censored
5	Death before first PD assessment	Date of death	Event
6	Death between adequate assessment visits ^a	Date of death	Event
		Date of last adequate radiologic assessment before missed tumor assessments	Censored

CR = complete response, PD = disease progression, PFS = progression-free survival, PR = partial response, SD = stable disease.

The priority of the censoring rules is as follows:

- 1. If the subject had PD or death, the following sequence will be applied:
- If a subject did not have a baseline tumor assessment (No. 1), the subject will be censored on the date of first dose. If the subject died within 125 days following first dose and did not receive a new anticancer treatment, it will be counted as an event at the date of death. If a subject had new anticancer treatment before PD or death (No. 4), the subject will be censored on the date of the last adequate tumor assessment prior to or on the date of new anticancer treatment.
- If a subject missed 2 or more tumor assessments (>125 days) before PD or death (No. 7), the subject will be censored on the date of the last adequate tumor assessment before PD or death. Note that if a subject is censored by both this criterion and the anticancer treatment criterion, the earliest censoring date will be used.

Eisai Confidential Page 28 of 30

a: Adequate tumor assessment is radiological assessment of CR, PR, SD, non-CR/non-PD or PD as determined by investigators at regular interval as defined in the protocol. Any tumor assessments after new anticancer treatment starts will be removed in the definition of PFS.

b: Defined in Appendix 13.1.

- Otherwise, if a subject had an event (No. 2, No. 5, or No. 6), the earliest event date will be used.
- 2. If a subject did not have PD or death, the censoring date will be the earliest censoring date if the subject met multiple censoring criteria (No. 1, No. 3, No. 4 or No. 7).

Eisai Confidential Page 29 of 30

SIGNATURE PAGE
